5.1 Laboratory assessment

Plasma samples will be collected in NVAf patients, after collection of written informed consent, within the first 15-30 days of treatment. During routine periodic checks, clinical information (weight, blood pressure, changes in clinical status and co-medications, creatinine clearance, blood count), and adverse events defined by the protocol (Appendix 2) will be recorded. The drug dose intake is recommended in the morning and evening for dabigatran and apixaban, and in the morning for rivaroxaban (during breakfast) and for edoxaban.

Blood sampling should be performed as follows:

1. at trough level for each anticoagulant drug used, in fasting subject: 12 hours or 24 hours after the last dose intake of dabigatran and apixaban, or of rivaroxaban and edoxaban, respectively. This blood sample is mandatory for the study.

It is up to the participating centres, depending on their availability and organization, to perform a blood sample at peak, after 2 hours of dose intake, or further blood samples at 3rd, 6th and 9th month of treatment.

See Appendix 3 for technical aspects of blood sampling and processing (19).

The frozen samples in anonymous form will be initially stored at the participating centre, then centralized and stored c/o the Biobank of Fondazione Arianna Anticoagulazione in Bologna for 5 years (compatibly with their quantitative availability). The following specific tests for DOAC levels measurement will be performed: dTT (diluted thrombin time) and ECA (Ecarin chromogenic assay) calibrated for dabigatran; chromogenic anti-Xa assays, calibrated for apixaban, rivaroxaban, or edoxaban. These assays are indirect methods that do not measure quantitatively DOAC concentrations (as the gold standard liquid chromatography-tandem mass spectrometry LC-MS/MS), but the biological activity of the drug. Nevertheless, many published studies have shown that the DOAC activity measured by coagulative and chromogenic methods is significantly correlated with the DOAC levels measured by LC-MS/MS (20-23), and their use is recommended by Italian (24) and international (8) guidelines.

All the dedicated methods available (from all the companies) will be assessed in laboratories identified by the Promoter to measure the anticoagulation level of the four direct oral anticoagulant drugs. Each assay, for all collected samples, will be carried-out in the same laboratory for that assay (to avoid inter-laboratory variability). The tests will be carried out when

appropriate in relation to the optimal number of samples to be tested. Results of the tests will be kept blind both to attending clinicians and patients; they will be open to the participating centre only at the end of follow-up period.

5.2 Outcomes during the follow-up

5.2.1 Primary outcomes

1. Bleeding complications (Appendix 2): a composite of:
 - Major bleeding (ISTH definition) (17)
 - Clinically relevant non-major bleeding (18)
2. Thromboembolic complications (Appendix 2):
 - objectively documented cerebral vascular event
 - systemic embolism with angiographic demonstration of abrupt arterial occlusion
3. Mortality (cardiovascular and total)

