4.1 Enrolment procedure

The active participants will propose to participate in the study to the NVAf subjects treated with DOAC that satisfy the inclusion and exclusion criteria

4000 consecutive NVAf patients, 1000 for each single drug, aged >18 years and starting anticoagulation with one of the four DOAC (apixaban, dabigatran, edoxaban, rivaroxaban) will be enrolled at the moment of the first prescription. The enrolment will end at the achievement of 4000 patients, 1000 for each drug.

The study requires a mandatory plasma collection for the measurement of the anticoagulant activity of the drug at the steady state, that is within the first 2-4 weeks of treatment, obtained at the time of trough, immediately before the subsequent intake of the drug. It is up to the participating centres, depending on their availability and organization, to perform an additional plasma collection on the same day 2 hours after the last intake, or to make further blood sampling after 3, 6 or 9 months from the time of the first prescription.

The Italian FCSA guidelines recommend a follow-up visit approximately one month after the first prescription to confirm the necessary patient's adherence to the treatment and to complete the routine exams not available at the time of prescription. On that occasion, and together with the routine blood sampling, it will be collected the plasma needed to measure the DOAC concentration for the study, taking 10 ml more of blood. Samples will be treated and identified locally in order to

maintain patient's anonymity, later they will be centralized to the Biobank of Fondazione Arianna Anticoagulazione in Bologna (Italy). Afterwards, samples will be distributed to laboratories identified by the Promoter for the measurement of DOAC plasma concentration. Test results will be centrally stored and communicated to the patient's recruiting centre only at the end of the study. Each patient will have a 12-month follow-up period, that will start at the time of the plasma collection, established within 15-30 days from the beginning of DOAC treatment.

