5.2.2 Secondary outcomes

- Drug discontinuation
- Adverse drug reaction (determining change of treatment)
- Thromboembolic complications (venous and/or arterial)
- A composite of thromboembolic and total mortality
- A composite of bleeding complications and total mortality
- Incidence of thromboembolic/haemorrhagic complications by CHADS-Vasc subgroups

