6.2 Sample size

We estimate that the global incidence of thromboembolic events and bleeding complications to be around 2% and 10% in NVAF patients per year. The range of drug levels at trough or peak, from the quantification level to the highest measured level, will be divided into classes. Comparisons will be made by contrasting the first vs the fourth class (for efficacy: increased incidence of thromboembolism in the first vs last class; for safety: increased incidence of bleeding in the last vs first class). We assume that the incidence of thromboembolism is 6% in the first class, and 1% in the fourth class, thus requiring 211 patients per class (total 844) to demonstrate differences in the efficacy end point, with an alpha and beta error equal to 0.05 and 0.80, respectively. We assume that the incidence of bleeding is 8% in the first class, and 16% in the fourth class, thus requiring 252 patients per class (total 1004) to demonstrate differences in the safety end point, with an alpha and beta error equal to 0.05 and 0.80, respectively.

We therefore aim at evaluating 1000 NVAF patients per drug subgroup (total 4000 patients).

For the statistical analysis, follow-up will be interrupted and patients censored when:

- a primary outcome is reached
- therapy is definitively interrupted
- end of study

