- Inconclusive spiral CT, pulmonary angiography, or VQ scan evidence of a new or recurrent PE, with demonstration of a new or recurrent deep vein thrombosis (DVT) in the lower extremities by compression ultrasound (CUS) or venography.

Proximal deep vein thrombosis (DVT)

Symptoms of DVT with one of the following findings.

(a) For a NEW DVT: abnormal CUS, or an intraluminal filling defect on venography.

(b) For a RECURRENT DVT:

- abnormal CUS where compression had been normal or, if non-compressible during screening, a substantial increase (4 mm or more) in diameter of the thrombus during full compression, or
- an extension of an intraluminal filling defect, or a new intraluminal filling defect, or an extension of non-visualization of veins in the presence of a sudden cut-off on venography.

DEATH

For all patients who died during the study, the cause of death was adjudicated to one of the following categories.

- VTE-related death
 - ✓ PE (based on objective diagnostic testing, autopsy)
 - ✓ Unexplained death (and VTE cannot be ruled out)
 - ✓ Sudden death (and VTE cannot be ruled out).
- Cardiovascular (CV)-related death
 - ✓ Myocardial infarction (MI)
 - ✓ Stroke
 - ✓ Other CV event (to be specified).
- Other
 - ✓ Cancer
 - ✓ Bleeding

- ✓ Infectious disease
- ✓ Other known cause (to be specified).

BLEEDING EVENTS

Major bleeding event

A major bleeding event was defined as a bleeding event (as per International Society on Thrombosis and Haemostasis guidelines ¹¹), as follows.

- Acute clinically overt bleeding accompanied by one or more of the following.
 - ✓ a decrease in hemoglobin of 2 g/dl or more
 - ✓ a transfusion of 2 or more units of packed red blood cells
 - ✓ bleeding that occurs in at least one of the following critical sites: intracranial, intraspinal, intraocular, pericardial, intra-articular, intramuscular with compartment syndrome, retroperitoneal
 - ✓ fatal bleeding

Clinically relevant non-major bleeding event

The definition of clinically relevant non-major bleeding was acute clinically overt bleeding that consists of:

- any bleeding compromising hemodynamics
- any bleeding leading to hospitalization
- subcutaneous hematoma larger than 25 cm², or 100 cm² if there was a traumatic cause
- intramuscular hematoma documented by ultrasonography

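### Section 5.2.1 accepts systemic embolism in the primary thromboembolic outcome only on angiography, and Appendix 2 has no entry for it; the likely loss of events is small

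*Combined protocol and SAP*

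**What the plan says.** Section 5.2.1 lists two components of the primary thromboembolic outcome: an "objectively documented cerebral vascular event" and "systemic embolism with angiographic demonstration of abrupt arterial occlusion". No other proof is listed for the second. The item is headed "Thromboembolic complications (Appendix 2"), so the reader is sent to that appendix for definitions.

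Appendix 2 defines pulmonary embolism, proximal deep vein thrombosis, categories of death, and bleeding. It has no entry for systemic embolism or for stroke. For venous events it accepts several kinds of proof: CT, angiography, ventilation/perfusion scanning, ultrasound or venography, depending on the event. Under Death it lists "PE (based on objective diagnostic testing, autopsy") as a basis for a VTE-related death.

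Two other outcomes matter here. Mortality, cardiovascular and total, is the third primary outcome in 5.2.1. Section 5.2.2 lists "Thromboembolic complications (venous and/or arterial") as a secondary outcome, with no standard of proof.

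Section 8.2 states that clinical investigations are independent of the study, and 4.2 keeps follow-up in line with local usual care.

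**The concern.** Two components of one outcome are held to different standards, and no reason is given. Whether a systemic embolism counts depends on which test the treating hospital happened to use, and the study has no say in that choice. The text offers the Adjudication Committee no alternative route.

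At stake is the number of countable events in the rarer of the two clinical outcomes. Section 6.2 expects about 2% thromboembolism against 10% bleeding, and contrasts the first with the fourth drug-level class. With so few events, even a small avoidable loss is worth preventing if prevention costs almost nothing.

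**Working it through.** **Inputs from the documents**

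- Incidence, section 6.2: "We estimate that the global incidence of thromboembolic events and bleeding complications to be around 2% and 10% in NVAF patients per year".
- Patients, section 6.2: "We therefore aim at evaluating 1000 NVAF patients per drug subgroup (total 4000 patients").
- Follow-up, section 4.1: "Each patient will have a 12-month follow-up period, that will start at the time of the plasma collection".
- Efficacy contrast, section 6.2: 6% in the first class against 1% in the fourth, alpha 0.05, 211 per class. The stated beta of 0.80 is read as power.

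**Inputs assumed, because the documents give none**

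- Systemic embolism is 5-15% of thromboembolic events.
- 30-50% of systemic embolisms are documented without angiography.
- The 2% counts all objectively documented events. Its composition is not stated.
- Classes are equal, so 1000 / 4 = 250 per class. Section 6.2 only implies equal classes (844 / 4 = 211).

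**Step 1. Reproduce the plan's figure.** Two-sided test of two proportions, pooled variance under the null, no continuity correction:

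n = [1.96 × √(2 × 0.035 × 0.965) + 0.8416 × √(0.06 × 0.94 + 0.01 × 0.99)]² / (0.05)²
= [0.5094 + 0.2167]² / 0.0025 = 210.9, so 211 per class. This matches.

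**Step 2. Expected events.** 1000 × 0.02 × 1 year = 20 per drug; 4000 × 0.02 = 80 overall. Censoring at definitive interruption of therapy (6.2) would lower these somewhat.

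**Step 3. Events lost.** Loss fraction = share that is systemic embolism × share without angiography.

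| | Low | High |
|---|---|---|
| Loss fraction | 0.05 × 0.30 = 1.5% | 0.15 × 0.50 = 7.5% |
| Lost per drug (of 20) | 0.3 | 1.5 |
| Lost overall (of 80) | 1.2 | 6 |

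**Step 4. Loss in one drug's fourth class.** At the design rate, 250 × 1% = 2.5 events. The design rates with evenly spaced middle classes average (6% + 1%) / 2 = 3.5%. Scaled to the stated 2%, the fourth class becomes 1% × 2 / 3.5 = 0.57%, or 250 × 0.57% = 1.4 events. Expected loss runs from 1.4 × 0.015 = 0.02 to 2.5 × 0.075 = 0.19 events.

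**Step 5. Power, same test, 250 per class, both rates cut in proportion.**

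- No loss, 6% vs 1%: 86.3%.
- 1.5% loss, 5.91% vs 0.985%: 85.7%.
- 7.5% loss, 5.55% vs 0.925%: 83.4%.

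At the rates scaled to 2% overall (3.43% vs 0.57%), power is 62.7% with no loss and 59.2% with a 7.5% loss. The low starting value there comes from the event rate and not from the case definition.

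**Step 6. Wider range.** With a 5-20% share and 25-100% lacking angiography, 20 × 0.05 × 0.25 = 0.25 to 20 × 0.20 × 1 = 4 events per drug are lost. Power for 6% vs 1% falls from 86.3% to 85.8% at the low end and 77.5% at the extreme, where no systemic embolism has angiography.

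**The case against.** The strongest reply is that a strict objective criterion trades sensitivity for specificity, which is a defensible choice for a rare component. If the missed events are unrelated to drug level and false positives are rare, the ratio between classes is not biased and only a little power is lost. That stands, and it keeps the point small. It does not explain why the cerebral component has a looser standard or why the appendix is silent.

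Three further limits also stand.

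- The events are not lost to the study. A fatal embolism found at autopsy counts in primary mortality, and Appendix 2 has a category for other cardiovascular deaths. A non-fatal one can enter the secondary outcome in 5.2.2. Neither route puts it back into the primary thromboembolic outcome.
- The word angiographic is unqualified. If it covers CT and MR angiography, much non-invasive imaging is already accepted. Duplex ultrasound, surgery and autopsy are not covered on either reading.
- The shares in step 3 have no source in the documents.

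A reader might infer more: that angiography is avoided in poor renal function, that such patients have higher troughs, and that embolisms therefore go missing mainly from the highest class and exaggerate the contrast. The documents state neither link. Type and dosage are chosen on clinical characteristics (3.3), so a gradient of trough with renal function cannot be presumed, and levels are hidden from clinicians and patients (5.1), so work-up cannot respond to the measured level itself. Blinding does not rule out an indirect link through patient characteristics, but nothing in the plan establishes one. Even if the whole 7.5% loss fell on the fourth class alone, the ratio would move only from 6.0 to 6 / 0.925 = 6.5.

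A reader might also infer that one lost event decides the result. At the 2% rate, about 9 vs 1 events at 250 per class gives Fisher p = 0.020, and 9 vs 2 gives 0.063, so the contrast is fragile. But the expected fourth-class loss is 0.02-0.19 events, at least five times less than one.

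**Conclusion.** The point holds as a gap in the outcome definition and its ascertainment. It is not a sample-size error, since the plan's 211 per class reproduces, and it is not a demonstrated source of bias between level classes.

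Under the main assumptions the primary thromboembolic outcome loses 1.5-7.5% of its events, and power at the design rates stays above the planned 80%. Only the extreme of the wider range takes it below. The loss figures rest on the assumed shares, the power figures also on equal classes of 250 and on proportional loss. What rests on the text alone is the mismatch of standards within 5.2.1 and the missing appendix entry. This is a cheap improvement and does not threaten the study's conclusions.

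**What to change.** Reword the second thromboembolic component in 5.2.1 and add (there is none to edit) a matching entry in Appendix 2: systemic embolism is abrupt arterial occlusion objectively documented by angiography (conventional, CT or MR), duplex ultrasound, surgery or autopsy. This also settles what angiography covers and brings the component to the same standard as the cerebral one.

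Make the change before adjudication starts and before drug levels are unblinded. Section 4.1 has the Adjudication Committee consider events together with the measured drug activity, and a definition widened after that would be open to challenge.

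The cost is one sentence in 5.2.1 and one entry in Appendix 2. No extra test, visit or patient is needed, and treatment is not touched. The downside is a slightly broader case definition for the adjudicators to apply.

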5.2.2 Secondary outcomes

- Drug discontinuation
- Adverse drug reaction (determining change of treatment)
- Thromboembolic complications (venous and/or arterial)
- A composite of thromboembolic and total mortality
- A composite of bleeding complications and total mortality
- Incidence of thromboembolic/haemorrhagic complications by CHADS-Vasc subgroups

5.3 Safety control

Every 6 months data regarding the events occurred in the interval period and the possible relationship with the individual results of drug levels measured at inclusion will be communicated to the Safety Committee. The Safety Committee, nominated by the Promoter, may propose the interruption of the study in case of excessive outcomes in relation to the drug levels results.

5.4 Results of the study

The study will evaluate DOAC plasma concentrations. In particular, dabigatran levels will be measured by dTT (diluted thrombin time) or ECA (chromogenic test for anti-IIa activity), while apixaban, edoxaban and rivaroxaban levels will be measured by a chromogenic method for anti-Xa activity. The possible relationship between DOAC plasma concentrations and the occurrence of haemorrhagic or thrombotic events during follow-up will be examined.

6. Statistical Considerations

6.1 Bias

To avoid patient's selection bias, the investigators are asked to consecutively include the observed patients or, if it is not possible, to declare the criterion adopted for enrolment (e.g. one day a week, one week a month, etc.).

6.2 Sample size

We estimate that the global incidence of thromboembolic events and bleeding complications to be around 2% and 10% in NVAF patients per year. The range of drug levels at trough or peak, from the quantification level to the highest measured level, will be divided into classes. Comparisons will be made by contrasting the first vs the fourth class (for efficacy: increased incidence of thromboembolism in the first vs last class; for safety: increased incidence of bleeding in the last vs first class). We assume that the incidence of thromboembolism is 6% in the first class, and 1% in the fourth class, thus requiring 211 patients per class (total 844) to demonstrate differences in the efficacy end point, with an alpha and beta error equal to 0.05 and 0.80, respectively. We assume that the incidence of bleeding is 8% in the first class, and 16% in the fourth class, thus requiring 252 patients per class (total 1004) to demonstrate differences in the safety end point, with an alpha and beta error equal to 0.05 and 0.80, respectively.

We therefore aim at evaluating 1000 NVAF patients per drug subgroup (total 4000 patients).

For the statistical analysis, follow-up will be interrupted and patients censored when:

- a primary outcome is reached
- therapy is definitively interrupted
- end of study

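### Section 6.2 misstates its design figures (4 × 252 is 1,008, not 1,004; the 0.80 is power, not beta) and leaves open whether 1,000 per drug means enrolled or evaluable patients

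*Combined protocol and SAP*

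**What the plan says.** Section 6.2 sizes two contrasts between the first and fourth classes of drug level.

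- **Thromboembolism**, 6% versus 1%: "thus requiring 211 patients per class (total 844) to demonstrate differences in the efficacy end point".
- **Bleeding**, 8% versus 16%: "thus requiring 252 patients per class (total 1004) to demonstrate differences in the safety end point".
- **Error rates**, in the same words for both: "with an alpha and beta error equal to 0.05 and 0.80, respectively". Sidedness and formula are not given.
- **Classes**: "The range of drug levels at trough or peak, from the quantification level to the highest measured level, will be divided into classes". The section does not say whether they are equal in size.
- **Target**: "We therefore aim at evaluating 1000 NVAF patients per drug subgroup (total 4000 patients"), with no inflation for losses.
- **Censoring**: "For the statistical analysis, follow-up will be interrupted and patients censored when" a primary outcome occurs, "therapy is definitively interrupted", or the study ends. This applies to both endpoints.

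Section 4.1 states: "The enrolment will end at the achievement of 4000 patients, 1000 for each drug". Patients are enrolled at first prescription, and the mandatory trough sample follows 2-4 weeks later. Section 6.3 then excludes patients whose sample is missing or cannot be tested, and patients without clinical follow-up. The documents give no expected exclusion rate and no replacement rule.

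**The concern.** Two printed figures cannot be right as they stand: the bleeding total is not four times its class size, and a beta error of 0.80 would mean a study planned to miss a true difference four times in five.

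The third matter is the link between the sample size and who is counted. Patients enter before it is known whether they will have a usable sample or any follow-up. If the 1,000 at which enrolment stops are enrolled patients, fewer will be analysed, and the bleeding contrast has no reserve. A reader who takes the 80% at face value could then give too much weight to a null bleeding result for a single drug.

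**Working it through.** **Inputs.** From section 6.2: the four risks, alpha 0.05, 211 and 252 per class, totals 844 and 1,004, and 1,000 per drug. From section 4.1: the enrolment stop. Assumed: a two-sided test (the one-sided formulas give 199-228 for bleeding and do not reproduce 252) and, except in step 6, equal classes.

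**1. Reproducing the class sizes.** Here z₁ = 1.960, z₂ = 0.842 for power 0.80, and p̄ is the mean of p₁ and p₂.

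Pooled formula: n = [z₁√(2p̄(1−p̄)) + z₂√(p₁(1−p₁)+p₂(1−p₂))]² / (p₁−p₂)²

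- 6% vs 1%: [1.960 × 0.2599 + 0.842 × 0.2575]² / 0.05² = 210.9, so 211, as printed.
- 8% vs 16%: [1.960 × 0.4596 + 0.842 × 0.4561]² / 0.08² = 257.8, so 258.

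Arcsine formula: n = 2[(z₁+z₂)/h]², with h = 2|arcsin√p₁ − arcsin√p₂|

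- 8% vs 16%: h = 0.2495, n = 252.1, which fits the printed 252.
- 6% vs 1%: h = 0.2946, n = 180.9, which does not fit 211.

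So each printed size can be reproduced at power 0.80, but not both to the patient by one of these formulas.

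**2. Totals.** 4 × 211 = 844, as printed, so the multiplier is four. 4 × 252 = 1,008, not 1,004. The slip could instead lie in the 252, since 4 × 251 = 1,004, but neither formula gives 251. With the pooled formula throughout, the total would be 4 × 258 = 1,032.

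**3. The beta label.** Beta 0.80 means power 0.20, so z₂ = −0.842. The pooled formula then gives 34.3 and 41.7 per class, against the printed 211 and 252.

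**4. Power at the planned number.** 1,000 / 4 = 250 per class.

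Pooled: power = Φ{[|p₁−p₂|√n − z₁√(2p̄(1−p̄))] / √(p₁(1−p₁)+p₂(1−p₂))}

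Arcsine: power = Φ{h√(n/2) − z₁}

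For bleeding at n = 250, pooled: Φ{(0.08 × 15.811 − 0.9007) / 0.4561} = Φ(0.799) = 78.8%.

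| Loss (assumed) | n per class | Bleeding, pooled | Bleeding, arcsine | Thromboembolism, pooled |
|---|---|---|---|---|
| 0% | 250 | 78.8% | 79.7% | 86.3% |
| 5% | 237.5 | 76.7% | 77.6% | 84.5% |
| 10% | 225 | 74.4% | 75.4% | 82.5% |
| 20% | 200 | 69.3% | 70.4% | 77.9% |

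At the plan's own 252 per class, pooled power is 79.1%. The gap between 252 and 250 therefore costs about 0.3 points.

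**5. Censoring.** Every figure in the table is before censoring. As an illustration only, suppose 10% loss and observed risks 10% lower in every class. The pooled formula at 225 per class then gives 69.3% for bleeding (7.2% vs 14.4%) and 78.2% for thromboembolism (5.4% vs 0.9%).

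**6. Unequal classes.** With 500 patients in the two extreme classes but split 350/150 or 400/100 (assumed splits, no losses), pooled bleeding power is 74.2% or 65.4%.

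**The case against.** The strongest reply is that the target is expressed as patients evaluated, and that section 6.3 removes unusable patients from the study altogether, so they need not count towards 1,000. Section 4.1 does not say whether they count or are replaced. This stands: the exclusion shortfall is conditional on 1,000 meaning enrolled patients. The plan also limits losses. Availability for sampling and for 12 months of follow-up are entry criteria (3.3.1), the trough sample is mandatory, and missed visits are chased (4.2, 6.3). These steps reduce losses but do not make them zero.

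A second reply is that about one point of the bleeding deficit is the choice of formula. This also stands, which is why both formulas are shown.

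Three stronger readings are tempting and are not supported:

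- *Exclusions are what take bleeding power below 80%.* By either formula it is already just below 80% at 250 per class with no exclusions.
- *Censoring weakens only thromboembolism.* The rule in section 6.2 covers both endpoints.
- *The classes must be quartiles.* The totals assume equal classes, but the text divides the range of levels. With equal classes, and middle-class risks between the extremes, overall thromboembolism is at least (6+1+1+1)/4 = 2.25%, against a stated figure of around 2%. Overall bleeding reaches the stated 10% only if three classes all sit at 8%. Equal classes are not ruled out, but the sponsor has to say what is meant.

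**Conclusion.** The point holds and is minor. The total of 1,004 and the beta label are wrong as printed, and neither affects the conduct of the study. The enrolment stop is 4 patients below the stated bleeding requirement (8 below the corrected one), which is trivial.

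The part with practical weight is conditional. If 1,000 means enrolled, bleeding power per drug falls to about 74-75% at 10% loss and 69-70% at 20%. Thromboembolism keeps about 80% until losses reach roughly 15% (pooled, 212 per class: 80.2%). These figures rest on assumed loss rates, equal classes, the plan's own risks and no censoring. A reader might infer that the study is badly underpowered for bleeding. The documents do not support that, because they give no loss rate and do not settle which patients the 1,000 counts.

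**What to change.** Keep 1,000 per drug and restate section 6.2:

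1. Correct the bleeding total to 1,008, or use 258 per class and 1,032 with the pooled formula that gives 211. Name the formula.
2. Replace the error-rate wording with: two-sided alpha 0.05, power 0.80 (beta 0.20).
3. State whether 1,000 per drug is enrolled or evaluable, in agreement with section 4.1. If enrolled, give the expected exclusion rate and replace the 80% bleeding claim with the power at the expected evaluable number. At an assumed 10% loss, for example, that is about 74% (pooled) or 75% (arcsine) at 225 per class.
4. Describe the power for both endpoints as before censoring.
5. State how the four classes are formed, noting that 844 = 4 × 211 assumes equal sizes. If they will not be equal, restate the power for the expected class sizes.

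The cost is wording only: no extra patients and no change to data collection. The stated bleeding power becomes less favourable.

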- epistaxis that lasted for more than 5 minutes, was repetitive (i.e. two or more episodes of bleeding more extensive than spots on a handkerchief within 24 hours), or led to an intervention (e.g. packing or electrocoagulation)
- gingival bleeding occurring spontaneously (i.e. unrelated to eating or tooth brushing) or lasting for more than 5 minutes
- hematuria that was macroscopic and was spontaneous or lasted for more than 24 hours after instrumentation (e.g. catheter placement or surgery) of the urogenital tract
- macroscopic gastrointestinal hemorrhage, including at least one episode of rectal blood loss, if more than a few spots on toilet paper
- hemoptysis, if more than a few speckles in the sputum and not occurring within the context of PE
- any other bleeding type considered to have clinical consequences for a patient such as medical intervention, the need for unscheduled contact (visit or telephone call) with a physician, or temporary cessation of a study drug, or associated with pain or impairment of activities of daily life

Minor bleeding events

All acute clinically overt bleeding events not meeting the criteria for either major bleeding or clinically relevant non-major bleeding were classified as minor bleeding.

Fatal bleeding event

A fatal bleeding event was defined as a bleeding event that the adjudication committee determined was the primary cause of death or contributed directly to death.

APPENDIX 3

Sample collection protocol

1. Select the patient treated with one of the direct acting oral anticoagulants, which you want to include in the study. Besides other characteristics (see protocol for further details) the patient must express (after appropriate information) the availability to perform a trough and a peak (optional) withdrawal, to be carried out preferably in the morning, just before taking the daily dose (or one of two daily doses, for double-dose drugs). Trough withdrawal should be performed 12 hours after the last dose of dabigatran or apixaban and 24 hours after the last intake of rivaroxaban or edoxaban.
2. For each sample it is required a total blood volume of 9-10 ml (e.g. 2 tubes of 4.5 ml or 4 tubes of 2.7 ml), taken with a vacuum system, containing citrate at the concentration of 0.109 M (3.2%).
3. Centrifuge (within 2 hours from sampling) for 15 minutes at 2,000xg at controlled room temperature (20°C).

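### Read literally, the censoring rule in section 6.2 lets a non-major bleed end follow-up for thromboembolism and death, so primary-outcome events that the study collects are discarded

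*Combined protocol and SAP*

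**What the plan says.** The censoring rule stands at the end of section 6.2 (Sample size). It begins "For the statistical analysis, follow-up will be interrupted and patients censored when" and lists three cases: "a primary outcome is reached", "therapy is definitively interrupted", and the end of the study. It does not say which primary outcome is meant, or whether the rule also governs the secondary outcomes.

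Section 5.2.1 lists three primary outcomes:

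- bleeding, a composite of major and clinically relevant non-major bleeding;
- thromboembolism, defined by "objectively documented cerebral vascular event" or systemic embolism;
- mortality, cardiovascular and total.

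The non-major definition in Appendix 2 includes events as mild as "gingival bleeding occurring spontaneously (i.e. unrelated to eating or tooth brushing) or lasting for more than 5 minutes".

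Section 5.2.2 adds secondary outcomes, among them "Drug discontinuation" and two composites that include total mortality. Sections 4.1 and 4.2 have all events recorded for 12 months after sampling, also in patients who stop treatment. Section 6.3 describes the analysis as the distribution of events in relation to drug levels and a study of correlations. It names no time-to-event, rate or competing-risk method.

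**The concern.** Bleeding and thromboembolism are separate outcomes with opposite hypotheses: section 6.2 expects more thromboembolism at low levels and more bleeding at high levels. A rule that stops at whichever primary outcome comes first lets one outcome cut off observation of the others. A patient with a gum bleed who stays on the drug would no longer be at risk of stroke in the analysis. A patient who has a stroke and dies some weeks later would contribute no death.

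The plan assumes twice as much bleeding in the fourth class as in the first, so the time lost for thromboembolism depends on the exposure under study. At stake are the completeness of two primary outcomes and, under some analysis methods, the size of the efficacy contrast.

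**Working it through.** **Inputs from section 6.2.** One-year thromboembolism 6% (first class) and 1% (fourth class); one-year bleeding 8% and 16%; 1000 patients per drug; overall rates of 2% and 10%. **Assumptions.** Constant hazards over the year, independent except where stated; four equal classes of 250 per drug; deaths ignored, because the plan gives no death rate.

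**Step 1. The plan's own figure.** Two-sided alpha 0.05, power 80%, pooled variance, mean proportion 0.035:

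n = [1.960·√(2·0.035·0.965) + 0.842·√(0.06·0.94 + 0.01·0.99)]² / 0.05² = 211 per class, as stated. The efficacy calculation is therefore consistent with a comparison of two proportions.

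**Step 2. Hazards,** λ = −ln(1 − p).

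- First class: λT = 0.0619, λB = 0.0834, sum 0.1453.
- Fourth class: λT = 0.0101, λB = 0.1744, sum 0.1844.

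**Step 3. Thromboembolism observed under the literal rule,** λT/(λT+λB) × [1 − exp(−(λT+λB))].

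- First class: 0.426 × 0.1352 = 5.76% (true 6%). Lost: 0.24/6 = 4%, or 0.6 of 15 events per 250.
- Fourth class: 0.0545 × 0.1684 = 0.92% (true 1%). Lost: 0.08/1 = 8%, or 0.2 of 2.5 events per 250.

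Bleeding stops the clock first in about 19 and 40 of 250 patients. The person-time lost is also about 4.0% and 8.2%. For a whole drug group, 2% of 1000 gives 20 events. With 10% bleeding and on average half a year lost, about 5% of these, or one event, is discarded.

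**Step 4. Effect on the contrast, crude proportions.** The ratio, from unrounded values, is 6.27 instead of 6.0. The difference is 5.76 − 0.92 = 4.84 points instead of 5.00. Power at 250 per class falls from 86.3% to 85.6%, and the number needed rises from 211 to 215. If true thromboembolism is 2% in both classes, the spurious ratio is 1.05 and the two-sided rejection rate about 5.1%.

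**Step 5. Rate or Kaplan-Meier analysis.** With independent hazards, the rates under the rule are 0.0576/0.931 = 0.0619 and 0.00918/0.913 = 0.0101, the same as λT. There is no bias.

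**Step 6. Sensitivity.** Let the thromboembolic hazard be multiplied by k after a bleed, with the total one-year risk held at 6% and 1%. The pre-bleed hazard λ0 solves

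p = λ0/(λ0+λB)·[1 − exp(−(λ0+λB))] + ∫₀¹ λB·exp(−(λ0+λB)t)·[1 − exp(−kλ0(1−t))] dt.

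The crude analysis sees only the first term; Kaplan-Meier sees 1 − exp(−λ0). The documents give no value for k.

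| k | Crude ratio | Crude difference (points) | Kaplan-Meier ratio | Kaplan-Meier difference (points) |
|---|---|---|---|---|
| 1 | 6.27 | 4.84 | 6.00 | 5.00 |
| 2 | 6.54 | 4.70 | 6.25 | 4.85 |
| 3 | 6.78 | 4.56 | 6.48 | 4.72 |
| 5 | 7.24 | 4.33 | 6.93 | 4.48 |

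**Step 7. Mortality.** Deaths after a non-fatal bleed or stroke fall after the cut-off under any method. Without a death rate in the plan, this loss cannot be sized.

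**The case against.** The wording can be read more kindly. Section 6.2 sets up separate efficacy and safety contrasts, so the outcome meant may be the one under analysis. The term censored is itself loose, since taken strictly it would remove the outcome as an event. This is fair, but no other section limits the rule, and two analysts could derive different event counts from the same database.

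A reader might infer that the rule biases the efficacy contrast in favour of the study hypothesis. The documents do not support that. Censoring that differs between classes is not in itself a bias; it must also be informative within a class, or the analysis must use crude proportions. The direction also depends on the scale: the ratio rises, while the difference and the power fall slightly. An apparent ratio near 6.7 needs roughly a threefold thromboembolic risk after a bleed, which no figure in the plan supports. Section 6.3 does count short follow-up only for the period available, which fits person-time analysis, but it stops short of naming one.

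Three further limits stand. The 8% and 16% are for all bleeding, so the share due to non-major bleeds is unknown. Major bleeding is not listed as a separate outcome in sections 5.2.1 or 5.2.2, so the loss of later major bleeds from a count of their own is not a fault of this plan. And the text does not say that the rule applies to discontinuation or other secondary outcomes, so an undercount there is possible but not established.

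**Conclusion.** The point holds as a fault in a stated rule, with a small effect on the efficacy contrast. Followed literally, the rule discards collected primary-outcome events: about 4% and 8% of thromboembolic events in the first and fourth classes, and an unknown number of deaths. With crude proportions the ratio moves from 6.0 to 6.27 and the difference from 5.00 to 4.84 points. With rates or Kaplan-Meier there is no bias if a bleed leaves thromboembolic risk unchanged, and some bias if it does not. The plan does not secure the unbiased case because it names no method. These sizes rest on the plan's class rates, constant hazards and, for counts and power, four equal classes. Nothing here suggests that the rule invalidates the study.

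**What to change.** Replace the first bullet of the rule in section 6.2 with a rule for each outcome:

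- The bleeding analysis ends at the first bleeding outcome.
- The thromboembolism analysis ends at the first thromboembolic outcome, and patients stay at risk after a bleed.
- Mortality and the secondary outcomes are not cut off by an earlier non-fatal bleeding or thromboembolic event.
- Death is treated as a competing event in the analyses of non-fatal outcomes, and section 6.3 names the method.

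The bullet on definitive interruption of therapy needs a remark of its own. If a bleed leads to stopping, that bullet still censors thromboembolism after the bleed, so the new rules alone do not remove all informative censoring. State this, and add a sensitivity analysis that uses all events over the full 12 months regardless of treatment stop.

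The cost is a paragraph or two of text and slightly more analysis work. No new data are needed, because section 4.2 already follows patients for 12 months.
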